8.2 Definitions of DLT

Toxicity will be evaluated according to the NCI CTCAE, Version 5.0.

Nonhematologic TEAEs of NCI CTCAE Grade ≥ 3 clearly unrelated to the underlying disease and occurring during the first cycle will be considered DLTs (see Section 10.2 for relatedness guidance), with the following exceptions:

- Asymptomatic laboratory changes (other than renal and hepatic laboratory values, and Grade 4 lipase/amylase) that can be successfully supplemented (reversion of Grade 4 events to Grade ≤2, reversion of Grade 3 events to Grade ≤1 or baseline) within 72 hours.
- Grade 3 nausea/vomiting that can be managed subsequently with antiemetics (Grade 3 nausea or vomiting that persists beyond 48 hours with or without appropriate medical intervention will be considered a DLT).
- Grade 3 fatigue lasting less than 72 hours.
- Grade 3 elevation of alanine aminotransferase (ALT) or aspartate aminotransferase (AST) that resolves to Grade ≤1 or baseline within 7 days.
- Grade 3 IRR that responds to symptomatic treatment, without recurrence of Grade 3 symptoms.

The following hematologic TEAEs Grade ≥3 clearly unrelated to the underlying disease and occurring during the first cycle will be considered DLTs:

- Grade \geq 3 hemolysis.
- Grade 4 neutropenia lasting more than 7 consecutive days.
- Grade 4 thrombocytopenia lasting more than 14 consecutive days.
- Grade 3 thrombocytopenia with clinically significant bleeding.
- Any other Grade ≥4 hematologic toxicity with the exception of Grade 4 lymphopenia.

An incomplete recovery from treatment-related toxicity causing a >2-week delay in the next scheduled infusion before the initiation of Cycle 2 will be considered a DLT.

In Part 1, DLTs are events meeting the criteria above that occur before Cycle 2 Day 1 administration. Related TEAEs meeting DLT definitions occurring in later cycles or in Phase 2 (DLT-like events) will determine the suitability of the MTD/OBD dose for future studies.

Dose and schedule modifications for toxicity are described in Section 8.4.

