8.4.2 Criteria for Beginning or Delaying a Subsequent Treatment Cycle

Treatment with modakafusp alfa will use a cycle length of 28 days (21 days for Schedule C). For a new cycle of treatment to begin, the patient must meet the following criteria:

- Absolute neutrophil count must be ≥1000/mm³. Granulocyte-colony stimulating factor (G-CSF) can be used to reach this level.
- Platelet count must be $\geq 50,000/\text{mm}^3$.

For therapy to resume, toxicity considered to be related to treatment with modakafusp alfa must have resolved to Grade ≤1 or baseline (Grade 2 for platelets), or to a level considered acceptable by the physician. If the patient fails to meet the above-cited criteria for retreatment, initiation of the next cycle of treatment should be delayed for 1 week. At the end of that week, the patient should be re-evaluated to determine whether the criteria for retreatment criteria have been met. If modakafusp alfa cannot be administered as scheduled, the patient can continue taking the weekly dexamethasone doses unless the investigator considers that it is in the patient's best interest to also hold dexamethasone.

If there is a delay of a subsequent cycle longer than 2 weeks because of a related AE, the patient may be withdrawn from treatment unless there is clinical benefit as assessed by the investigator, with agreement by the sponsor. Modakafusp alfa dosing may be continued at the previously established safe dose level or below.

For modakafusp alfa infusions within the same cycle (Schedules A and B [once every 2 weeks (Q2W)]), the decision to hold treatment is left to investigator discretion based on clinical and analytical data and based on the toxicity that the patient presented with previous infusions in the same cycle. The investigator should differentiate from acute toxicity (eg, an IRR) from which the patient has recovered at the time of the next infusion or subacute toxicity (eg, neutropenia) that might worsen with another infusion if it is not in a clear recovery path. If the dose cannot be administered on the scheduled day, the patient can be reviewed at the investigator's discretion in the following 48 hours. If modakafusp alfa cannot be administered within a cycle in this 48-hour window, the dose will be missed and the patient scheduled for the next administration per the schedule of events (SOE).

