The dose of modakafusp alfa will not be reduced for an individual patient during Cycle 1 unless a DLT has been declared and it is still possible for the patient to receive treatment within the remaining dosing period scheduled. In this case, the patient can complete Cycle 1 at a reduced dose level.

8.4.3.1 Parts 1 and 2

Table 8.a Parts 1 and 2 Dose Modification Recommendations for Modakafusp Alfa Toxicities

This table does not include guidance for management of bleeding TEAEs and IRRs. Refer to Table 8.e for the management of bleeding TEAEs and Table 8.g and Table 8.h for the management of IRRs.

Criteria	Action
Grade 1 AEs	No dose reductions or interruptions.
Grade 2 AEs	Treat according to local practice. Whether to hold treatment or to continue it at the same or a reduced dose (Table 8.d) is at the discretion of the investigator.
	Patients experiencing Grade 2 AEs considered related to study treatment that are not easily managed or corrected and are not tolerable to the patient, or AEs that are not acceptable in the investigator's judgment, should have study treatment interrupted until the AE resolves to Grade ≤1 or baseline and then restarted at the same dose or, depending on the toxicity, at the previous safe dose level or below.
Grade 3, Grade 4 (not life-threatening), and Grade 4 asymptomatic laboratory AEs	Hold modakafusp alfa until resolution to Grade ≤1 or baseline, and then resume treatment at either the same dose or a reduced dose level at the discretion of the investigator.
Grade 4 (life-threatening) AEs	Consider permanently withdrawing the patient from the study, except when the investigator determines that the patient is receiving clinical benefit and has discussed this with the sponsor. Treatment may be restarted at a reduced dose level or below when toxicity recovers to Grade ≤1 or baseline.
AEs of all grades	If treatment has been held for >14 consecutive days without resolution of the toxicity (to baseline or Grade ≤1), consider permanently discontinuing study treatment unless there is clinical benefit for the patient as assessed by the investigator and with sponsor's approval. Treatment can be resumed at a reduced dose level after resolution of AEs to Grade ≤1 or baseline.

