8.4.4 Criteria for Discontinuing Modakafusp Alfa

Potential discontinuations of modakafusp alfa should be discussed with the sponsor or contract research organization (CRO) before implementation.

Modakafusp alfa should be discontinued in patients experiencing an AE in Cycle 1 meeting criteria for a DLT for which the investigator considers that retreatment of the patient could be dangerous.

If the next cycle of modakafusp alfa is delayed for >14 days (>28 days for Part 3) because of modakafusp alfa—related toxicities, study treatment should be discontinued unless the investigator considers that the patient will receive benefit continuing in the study. Patients will

be evaluated 30 days (EOT visit) after the last dose of modakafusp alfa or right before the start of subsequent systemic anticancer therapy to permit the detection of any delayed TEAEs.

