3) An incomplete recovery from treatment-related toxicity causing a >2 -week delay in the next scheduled infusion before the initiation of Cycle 2 (or next cycle if after cycle 1) will be considered a DLT.	Any TEAEs with AEREL="RELATED" and AEACN="DOSE DELAYED" and the next dose was delayed for >14 days

Assumptions:

- 1) Hematologic AEs include the following PTs:

Hematology collection from protocol	Preferred term
Hematocrit	“Anaemia” “Hemolysis”
Hemoglobin	“Anaemia” “Hemolysis”
Leukocytes with differential	“Leukopenia” “White blood cell count decreased”
Neutrophils (ANC)	“Neutropenia” “Neutrophil count decreased” “Febrile neutropenia”
Platelet (count)	“Thrombocytopenia” “Platelet count decreased”
Lymphocytes	“Lymphopenia” “Lymphocyte count decreased”

Note: PTs may change with coding updates.

- 2) Only include TEAEs which are related to study drug.
- 3) Duration is calculated in days, not hours e.g. 48 hours = 2 days (This would check the day of AE and the next day).
- 4) For 'Clinically significant bleeding', this is included in the non-hematologic AE part. Considering 'clinically significant' as Grade 3 or higher. No need to check for the thrombocytopenia, that is checked via the laboratory data.

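### SAP Appendix C item 3 does not reproduce the protocol's >2-week-delay criterion for patients who never receive another dose, so the DLT-like frequency can be understated

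*SAP*

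**What the plan says.** Protocol 8.2 counts as a DLT: "An incomplete recovery from treatment-related toxicity causing a >2-week delay in the next scheduled infusion before the initiation of Cycle 2". The same section says that related events meeting a DLT definition in later cycles or in Phase 2 are DLT-like events and will decide whether the MTD/OBD is suitable for future studies. Their frequency is a secondary endpoint in Part 1 and Part 2 (SAP 5.1.2 and 5.2.2).

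SAP Appendix C puts the protocol wording in its left column, extended in item 3 to cycles after the first, and the program rule in its right column. The rule for item 3 joins three conditions with AND: AEREL is RELATED, AEACN is DOSE DELAYED, "and the next dose was delayed for >14 days". SAP 7.12.1 applies the algorithm after Cycle 1 in Parts 1 and 2. Cycle 1 DLTs in dose escalation are those identified by the investigator.

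Three places in the protocol say what happens after such a delay:

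- **8.4.4:** if the next cycle "is delayed for >14 days (>28 days for Part 3") because of drug-related toxicity, "study treatment should be discontinued unless the investigator considers that the patient will receive benefit continuing in the study".
- **8.4.2:** after a related delay of more than 2 weeks, "the patient may be withdrawn from treatment unless there is clinical benefit as assessed by the investigator", with sponsor agreement.
- **Table 8.a in 8.4.3 (Parts 1 and 2):** after a hold of more than 14 days without resolution, "consider permanently discontinuing study treatment unless there is clinical benefit for the patient as assessed by the investigator".

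**The concern.** The protocol criterion is anchored to the infusion that was scheduled. It does not require that a later infusion is given. The program rule is anchored to an action code and to a next dose. These agree for patients who resume late and can part company for patients who are stopped.

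The difference is not random. In Parts 1 and 2 the delay that creates the event is also the delay at which 8.4.4 points towards stopping. The rule as written therefore tends to keep patients who were re-dosed and to lose those who were not. An endpoint meant to inform the suitability of the dose would then err in one direction, towards better apparent tolerability.

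**Working it through.** The plan states no figure for this rule, so there is nothing to reproduce. The check applies item 3 literally and then asks what the other items recover.

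**Step 1. The rule on four constructed patients.** Inputs: the Q4W schedule (28 days), and delay = next dose date − (last dose date + 28), counted if delay > 14.

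- Resumed 48 days after the last dose, action delayed: 48 − 28 = 20 days. Counted, as 8.2 requires.
- Resumed 42 days after the last dose, action delayed: 42 − 28 = 14 days. Not counted, as 8.2 requires.
- Stopped, action delayed: there is no next dose date, the delay cannot be computed, and the SAP gives no rule. Not counted on a literal reading.
- Stopped, action withdrawn: fails the AEACN filter. Not counted. SAP 7.7 lists withdrawn and delayed as separate actions.

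If toxicity held the dose past scheduled date plus 14 days in the last two patients, both meet 8.2.

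**Step 2. What other items catch.** Item 1 takes related nonhematologic events of Grade 3 or higher, with listed exceptions, and renal or hepatic laboratory values of Grade 3 or higher. Item 2e takes Grade 4 platelets or neutrophils that have not recovered by the scheduled dose date, and other Grade 4 hematology values except lymphocytes. Neither reaches a prolonged Grade 3 cytopenia or a lower-grade nonhematologic toxicity that holds dosing. Such holds are possible: 8.4.2 blocks a cycle below 50,000 platelets or 1000 neutrophils per mm³, and asks that other related toxicity resolve to Grade 1 or less, to baseline, or to a level the physician accepts. These patients reach the endpoint only through item 3.

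**Step 3. Size, as an illustration of item 3 counts only.** Let q be the share of patients with a related delay of more than 14 days who are then stopped. Item 3 reports true events × (1 − q). The documents do not give q. Assume 4 true item 3 events in a 25-patient cohort (4/25 = 16%):

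- q = 25%: 4 × 0.75 = 3, or 12%
- q = 50%: 4 × 0.50 = 2, or 8%
- q = 75%: 4 × 0.25 = 1, or 4%

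The loss on the full DLT-like endpoint is smaller to the extent that items 1 and 2e count the same patients.

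**Step 4. Whether the AE end date can serve as the recovery test.** Scheduled date plus 14 falls on day 28 + 14 = 42 after the last dose for Q4W and on day 21 + 14 = 35 for Q3W. SAP Appendix B imputes the end date of an ongoing AE as no later than last dose + 30 days. Since 30 < 35 < 42, an ongoing toxicity in a stopped Q3W or Q4W patient would look resolved before the cutoff. A test on imputed end dates would therefore miss the patients it is meant to find.

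**The case against.** The strongest reply is that item 3 says the next dose was delayed, not that it was given. Protocol 8.4.4 itself speaks of a delayed cycle that has not yet been given. A programmer could treat a dose never given as delayed by more than 14 days. That stands as a possible reading, but the SAP does not state it, and it would not help a patient whose action is recorded as withdrawn.

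Several other points also stand:

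- Only 8.4.4 uses the stronger wording (should, unless). Section 8.4.2 and Table 8.a are weaker, so stopping cannot be called the protocol's settled default.
- Protocol 4.6.2 says toxicities were handled with delays and supportive care and seldom led to discontinuation. That does not give q, but it limits how many patients can be missed.
- Stopped patients are still reported. TEAEs leading to discontinuation are tabulated (SAP 7.12.1), listed (SAP Appendix A) and a Part 1 primary endpoint (SAP 5.1.1).

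A reader might go further and infer that all stopped patients are lost and that the bias grows with toxicity. The documents do not support that, because items 1 and 2e pick up most severe cases. A reader might also link the gap to the DLT at 6 mg/kg, where a delay of more than 2 weeks helped to define the MTD (Protocol 4.6.2). That delay preceded Cycle 2, so it was a Cycle 1 DLT and lies outside this algorithm.

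**Conclusion.** The rule and the criterion it is meant to implement do not match for patients who receive no further dose. Exclusion is certain on the SAP text when the action is recorded as withdrawn. It is the natural but not the only reading when the action is recorded as delayed. The documents do not say how a delay followed by withdrawal is coded, so the split between the two cases is unknown.

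The consequence is a possible understatement of the programmed DLT-like frequency in Parts 1 and 2 after Cycle 1, confined to patients reachable only through item 3. No estimate of its size is possible from the documents, and the percentages above are not one. The investigator-identified Cycle 1 DLTs, the MTD decision and Part 3 are not touched. The point is worth correcting because the error can only run one way and affects a named secondary endpoint.

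**What to change.** Extend item 3 to related TEAEs with action delayed, interrupted or withdrawn where either of these holds:

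- the next dose was given more than 14 days after the scheduled dose date, as item 2e already defines that date; or
- no further dose was given by scheduled date plus 14 days, and at the last available assessment the toxicity had not met the protocol's own retreatment criteria.

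Judge recovery from the recorded grade, outcome or laboratory values, not from the Appendix B imputed end date. Flag patients with no assessment after the scheduled date and report the count with and without them. Count each patient-episode once across items 1 to 3. With this rule both stopped patients in the check would count if unrecovered, and the two who resumed would be classified as before.

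Separately, Protocol 8.4.2, 8.4.4 and Table 8.a should be reconciled on what follows a delay of more than 14 days. No view is taken here on which is right.

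The cost is a modest programming change and some cases with incomplete data. AE reporting generally ends 30 days after the last dose (Protocol 10.3), and end-of-treatment laboratory tests are due by then (Protocol Appendix A). That leaves 30 − 28 = 2 days after the scheduled date for Q4W and 30 − 21 = 9 days for Q3W. The weekly re-evaluation during a hold (Protocol 8.4.3) should fill part of that gap.

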Appendix D Operating Characteristics of the Futility Stopping Rules

Based on the proposed two interim futility analyses criteria (Section 7.13), the design operating characteristics were calculated for each of the treatment arms under different true ORR scenarios.

Appendix D Table 1 displays the corresponding operating characteristics for the treatment arm of 240 mg, including cumulative probability of terminating the arm early at each interim analysis, average number of patients enrolled and followed up for 3 months, average number of responders observed, and probability of success (PoS) at primary analysis. As there is no plan for efficacy claim based on any of the interim analyses, the only time to claim a positive efficacy conclusion (success for each arm) will be at the primary analysis. The success criterion will be a minimal of 33 responders among 118 treated patients, achieving the goal of lower limit of 95% CI above 20% uninteresting rate.

Appendix D Table 1 Operating Characteristics for the Treatment Arm of 240 mg

True ORR	Cumulative probability of terminating the arm early at		PoS at primary analysis	Average number of patients enrolled and followed up for 3 months	Average number of observed responders
	1 st IA for Futility	2 nd IA for futility			
10%	82%	99%	0%	21	2
20%	40%	70%	2%	56	11
30%	13%	19%	64%	101	30
35%	6%	8%	89%	111	39
40%	3%	3%	97%	115	46
50%	<1%	<1%	100%	118	59

IA: interim analysis; ORR: objective response rate; PoS: probability of success.

As shown in Appendix D Table 1, when the true ORR is 20%, there is about 40% chance to terminate the 240 mg arm at the first interim futility analysis; about 70% chance to terminate the arm at either the first or second interim futility analysis; probability of success at primary analysis is around only 2%. When the true response rate is 35%, the cumulative probabilities of terminating the arm are reduced to 6% and 8% at the first and second interim futility analyses, the probability of success at primary analysis is 89%.

A similar operating characteristics table was created for the treatment arm of 120 mg (Appendix D Table 2Appendix D).

Appendix D Table 2 Operating Characteristics for the Treatment Arm of 120 mg

True ORR	Cumulative probability of terminating the arm early at		PoS at primary analysis	Average number of patients enrolled and followed up for 3 months	Average number of observed responders
	1 st IA for Futility	2 nd IA for futility			
10%	55%	99%	0%	30	3
20%	17%	66%	2%	67	13
30%	4%	13%	68%	108	32
35%	1%	4%	93%	115	40
40%	1%	1%	99%	117	47
50%	<1%	<1%	100%	118	59

IA: interim analysis; ORR: objective response rate; PoS: probability of success

Similarly, as shown in Appendix D Table 2, when the true ORR is 20%, there is about 17% chance to terminate the 120 mg arm at the first interim futility analysis; about 66% chance to terminate the arm at either the first or second interim futility analysis; PoS at primary analysis is around only 2%. When the true response rate is 35%, the cumulative probabilities of terminating the arm are reduced to 1% and 4% at the first and second interim futility analyses, the PoS at primary analysis is about 93%.

Appendix E Statistical Guidance on Unacceptable Toxicity and Treatment Related Death

The Bayesian toxicity monitoring approach based on posterior probability will be implemented to each DMC data review up to the second interim futility analysis to continuously monitor the unacceptable toxicity (particularly for Grade ≥ 4 nonhematologic treatment-related TEAEs) and treatment-related death within each treatment arm separately at various time points.

These toxicity monitoring rules can be translated to toxicity boundaries in terms of the number of patients with Grade ≥ 4 nonhematologic treatment-related TEAEs and the number of treatment related death among all patients treated for each arm at each safety review. Appendix I Table 1 illustrates the toxicity boundaries with the expected numbers of treated patients for each IDMC safety review based on our most recent enrollment projection. The actual toxicity boundaries will be recalculated based on the observed number of treated patients at each safety review using the same posterior probability stopping rule.

Appendix E Table 1 Bayesian Toxicity Monitoring Boundaries for Grade ≥ 4 Nonhematologic Treatment-Related TEAEs and Treatment Related- Deaths for Each Treatment Arm

Number of treated patients per arm	Unacceptable toxicity if the number of patients with Grade ≥ 4 nonhematologic treatment-related TEAEs	Unacceptable toxicity if the number of patients with treatment-related death
10	≥ 4	≥ 1
35 ^a	≥ 11	≥ 3
65 ^a	≥ 20	≥ 5

^a The expected numbers of patients treated at IA1 and IA2 based on most recent enrollment projection.

Based on the toxicity boundaries presented in Appendix E Table 1, the corresponding operating characteristics for Grade ≥ 4 nonhematologic treatment-related TEAE monitoring for each treatment arm and the cumulative probability of early detection of unacceptable toxicity under different true toxicity rates with the expected number of patient treated at each safety review are displayed in Appendix E Table 2.

Appendix E Table 2 Operating Characteristics for Monitoring Grade \geq 4 Nonhematologic Treatment-Related TEAEs within Each Treatment Arm

True Toxicity rate	Cumulative probability of early detection with number of treated patients		
	10 patients	35 patients	65 patients
15%	5%	6%	6%
20%	12%	16%	17%
25%	22%	35%	39%
30%	35%	58%	67%
35%	49%	78%	88%

As shown in Appendix E Table 2, when the true toxicity rate is as low as 15%, there are low cumulative probabilities of 5% to 6% for early calls of unacceptable toxicity at each safety review; when the true toxicity rate is as high as 35%, there are about 49% to 88% cumulative probabilities of early call for unacceptable toxicity at each safety review. When the true DLT rate is 25% (the maximum toxicity allowed), there is about 39% cumulative probability to have an early call for unacceptable toxicity.

Similar operating characteristics table was created for monitoring of treatment-related death for each treatment arm, shown in Appendix E Table 3.

Appendix E Table 3 Operating Characteristics for Monitoring Treatment-Related Death within Each Treatment Arm

True Toxicity rate	Cumulative probability of early detection with number of treated patients		
	10 patients	35 patients	65 patients
1%	10%	10%	10%
3%	26%	29%	30%
5%	40%	48%	52%
7%	52%	64%	71%
9%	61%	76%	85%

As shown in Appendix E Table 3, when the true treatment-related death rate is as low as 1%, there is about 10% cumulative probability of early call of unacceptable toxicity at each safety review; when the true treatment related death rate is as high as 9%, there are about 61% to 85% cumulative probabilities of early toxicity call at each safety review. When the true treatment-related death rate is 5% (the maximum toxicity allowed), there is about 52% cumulative probability to alarm the unacceptable toxicity early.

